## A. SPECIFIC AIMS

Traumatic brain injury (TBI) is defined as “a bump, blow or jolt to the head or a penetrating head injury that disrupts the normal function of the brain.” Each year, more than 2.7 million U.S. people sustain a TBI. Despite high risks of readmission and complex medical needs, there are no U.S. standards of care for patients with moderate-to-severe TBI discharged home from acute hospital care without inpatient rehabilitation. Research suggests up to 65% of patients with moderate-to-severe TBI (age < 65 years) nationwide are discharged home from acute hospital care into a fragmented environment that does not integrate healthcare, community, and social services. These patients have cognitive, physical, behavioral, and emotional impairments that affect their abilities to independently self-manage their health, wellness, and activities of daily living and are often dependent on family who have difficulty managing the patient’s care and needs.

Transitional care is defined as actions in the clinical encounter designed to ensure the coordination and continuity of healthcare for patients transferring between different locations or levels of care in close geographic proximity. There are many factors that contribute to gaps in the transition from hospital to home, including inadequate planning, insufficient patient/family education, and limited and fragmented access to essential services. These gaps are often compounded by limited financial resources such as lack of insurance and lack of social support. Transitional care interventions can address these gaps with a variety of strategies, including individualized transitional care plans, post-discharge care coordination, and community-based service referrals. **Currently, there are no transitional care standards for TBI.** The discharge home from the hospital is an ideal intervention point to guide improvements in health and quality of life for patients with TBI and families; however, the current state of “usual care” has limited provider support or engagement to help patients and families navigate and access fragmented health and community-based services, is ineffective in improving functional outcomes, and does not incorporate family needs.

Thus, the purpose of our study is to develop, examine the feasibility and acceptability, and assess the preliminary efficacy of a patient- and family-centered TBI transitional care intervention to support patients with moderate-to-severe TBI and their family caregivers during the transition home from acute hospital care.

**The proposed specific aims are:**

**Specific Aim 1: To develop and refine a patient- and family-centered TBI transitional care intervention.**

The intervention will aim to improve functional status for patients with TBI, reduce strain for family caregivers, and direct patients and families to appropriate resources and care that is concordant with their health-related goals. We will use a combination of existing clinical guidelines, our prior and ongoing research, and a scoping review of care transitions literature to guide intervention development. We will create a manualized, intervention protocol that will undergo iterative user-testing with 6 focus groups (total 45-60 people) of patients with TBI, families, and healthcare providers to determine acceptability and to refine to ensure the intervention meets specific needs and preferences of patients with TBI and families.

**Specific Aim 2: To examine the feasibility and acceptability and assess the preliminary efficacy of the TBI transitional care intervention.**

The intervention will be tested with 15 dyads of patients with TBI discharged home from acute hospital care and their family caregivers. Recruitment, enrollment, data collection feasibility and intervention fidelity will be used to assess feasibility of implementation. We will develop a survey to assess acceptability. Preliminary efficacy will be estimated based on changes from baseline to intervention endpoint in the primary outcome of patient functional status at 8 weeks post-discharge (using Functional Status Examination). We will also examine secondary outcomes at 8 weeks post-discharge, including family caregiver strain and preparedness for the caregiving role and patient and family caregiver self-efficacy and healthcare utilization.

The proposed research is being submitted in response to NCMRR PAR-18-211 *Early Career Research Award* and directly aligns with the funding opportunity due to an early career scientist’s focus on repair and recovery of function in patients with TBI and behavioral modifications of patients with TBI and families. As directed by the funding opportunity announcement, the preliminary data generated from this proposed research will guide our team in designing and conducting an NIH R01 implementation-effectiveness clinical trial of the TBI transitional care intervention. Our team’s program of research has the potential to enhance the standard of care for patients with TBI discharged home from acute hospital care and their families.

## RESEARCH STRATEGY

### B. SIGNIFICANCE

**Devastating Effects of TBI.** Annually, more than 275,000 people sustain a moderate or severe TBI that requires hospitalization for  $\geq 2$  days immediately after injury. For those receiving TBI acute hospital care, typical discharge destinations include inpatient rehabilitation, skilled nursing facilities, or home. After acute hospital care, patients with TBI would ideally receive interdisciplinary, inpatient rehabilitation before returning home. Yet, up to 65% of patients with moderate-to-severe TBI nationwide are discharged directly home from acute hospital care without inpatient rehabilitation. Many patients with TBI who follow this care pathway are racial/ethnic minorities. Regardless of race, these individuals often return home with residual impairments in cognition, coordination and balance, and awareness and judgment and have increased risks for poor long-term outcomes. Up to 1 year after acute hospital care discharge home, patients with TBI have significant physical, mental, and social challenges that prevent return to pre-injury levels of functioning: 43% have long-term disabilities, 55% become depressed, and 60% never return to work. As the majority of patients with moderate-to-severe TBI sustain their injury at a young age, they must deal with these chronic physical, mental, and social challenges across their lifespan. These poor post-acute outcomes have tremendous implications for families of patients with TBI, especially for patients who were in school or working, may not yet be financially secure, and/or have small children. National data suggest TBI is also very expensive at multiple levels: the annual cost of TBI care is \$76.5 billion, of informal caregiving is \$6.1 billion, and lost productivity due to low rates of return to work equates to \$521 million. Recovery from TBI is a significant public health problem with harmful effects at multiple levels.

**Unmet Family Needs after TBI.** Family members of patients with TBI play a major role in supporting patients after discharge, yet, families report 30-60% of their needs after hospital discharge go unmet and that they feel ill-prepared to support the patient with TBI. Family members perceive the healthcare system to be difficult to navigate, unorganized, uncaring, and unresponsive. Research on family caregivers of patients with TBI also indicates family caregivers can have substantial unmet mental health needs. However, there is limited knowledge on family needs during the transition from acute hospital care to home, which is needed to provide guidance on how to manage the person with TBI's care and support their family.

**Gaps in Clinical Guidelines on Discharge and Follow-Up of Patients with TBI.** There are gaps in clinical guidelines related to transitional care of patients with TBI, regardless of severity, discharged home from acute hospital care. Although multiple U.S. guidelines have been published on care of patients with mild, moderate, or severe TBI, these guidelines have limited recommendations on discharge and follow up plans for supporting patients as they transition home from acute hospital care. In contrast, clinical guidelines from the United Kingdom (U.K.) do address transitional care needs related to discharge and follow-up of patients with TBI; the U.K. National Health and Care Excellence (NICE) clinical guidelines on discharge and follow-up of children, young people, and adults with head injury provide detailed guidance for healthcare providers involved in caring for patients with TBI in-hospital as they transition home or after discharge. The terms head injury and TBI are often used interchangeably. Although there are differences in health systems in the U.S. and the U.K., the patient population described in the U.K. NICE clinical guidelines are similar to the U.S. patients with moderate-to-severe TBI that are the focus of our study; the NICE clinical guidelines can provide a foundation for development of TBI transitional care interventions.

**Limitations of Current Transitional Care Research.** Effective transitional care can bring important benefits to patients and families. Transitional care interventions tested with patients with stroke, myocardial infarction, and heart failure have been effective in improving health outcomes and reducing disability and readmissions. However, the transition needs of patients with TBI discharged home from acute hospital care and their families are thought to be unique compared to other patient populations with acute conditions due to issues with: patient cognitive functioning, complex medical needs, and limitations in activities of daily living; family difficulty in managing care; and fragmented care and services with limited provider support. The few available TBI transitional care interventions were ineffective in improving functional outcomes for all patients with TBI; these interventions also did not include family needs or address patient and family behavior change or self-efficacy. In addition, the strength of evidence on TBI transitional care interventions is low due to shortcomings in study design and analysis, like: 1) lack of sufficient power to determine effectiveness and 2) use of multiple primary outcomes, which increases risk of false-positive errors. The transition from hospital to home after acute care is a critical period where appropriate supports and resources are necessary to increase the likelihood of successful recovery; however, research indicates coordinated transitional care, supports, and resources are lacking for patients with TBI and their families. Thus, new insights are needed to direct interventions to improve the TBI transition from acute hospital care to home for patients and families.

**Preliminary Research Related to Transitional Care of Patients with TBI and Their Families.** Our team's research provides evidence of the need for interventions to support the unique issues of patients with TBI and families in the transition home from acute hospital care, as well as effectiveness of transitional care interventions in improving functional status and quality of life in other patient populations. **Table 1** summarizes the 12 studies our research team has conducted, design/analytic approaches used, and key findings. Our team's research shows patients with TBI and families could benefit from interventions during the transition home that address issues with: 1) patient safety, independence, cognition, and communication; 2) management of the patient's mental health, overall health and wellness, and medications; 3) family needs; 4) access to community resources; and 5) behavior change and health-related goal activation. However, we have not yet developed or assessed the feasibility, acceptability, or preliminary efficacy of a transitional care intervention that addresses the above-listed areas, and research is limited on these topics.

Table 1. Our Research Team's Preliminary Research that Informs the Proposed Study			
Study Name	Team Member	Design/Approach	Key Findings
Mental health in women with TBI 	[name] (PI of R03)	Systematic literature review	Although being female is a risk factor for mental health issues, there is limited literature on sex-based disparities in mental health after TBI.
Hospital experience for patients and families 	[name] (PI of R03)	Systematic literature review	Studies showed during the hospital stay, patients with ABI and families had a high need for information, difficulty adjusting, a desire to be prepared for life after discharge, and mixed feelings on staff support.
Role of families in the TBI hospital stay 	[name] (PI of R03)	Qualitative: Grounded Theory	N=16. Families of patients with TBI perceived their role pre-discharge was to protect the patient's emotional and physical safety and had concerns about the patient's post-discharge independence.
Patient/family health, wellness, & safety 	[name] (PI of R03)	Qualitative: content analysis	N=27. Patients with TBI and families had a desire for provider support early post-discharge to manage mental health, overall health and wellness, medications, and patient safety.
Med. Management intervention 	[name] (PI of R03)	Experimental design	N=205. Patients with ABI and families in the treatment group had increased knowledge and confidence after educational intervention but had difficulty managing medications at 60-days post-discharge.
Nurses' perceptions of caring for TBI 	[name] (PI of R03)	Instrument + latent class analysis	N=713. 1) Instrument is reliable/valid for assessing nurses' perceptions of TBI care; and 2) Nurses had inaccurate perceptions and little knowledge of post-discharge resources for patients with TBI & families.
Consensus on provider discharge criteria 	[name] (PI of R03)	Survey research, descriptive	N=27. Criteria with majority consensus providers use to determine if a patient with TBI should go home from acute hospital care: 1) therapist recommendations (N=26); 2) plans for post-discharge family support (N=25); and 3) patient independence in activities of daily living (N=23).
Transition of care for acute stroke and MI 	[name] (Co-I of R03)	Systematic literature review	Studies showed hospital-initiated transitional care can improve some outcomes in adults with stroke or MI. More interventions are needed that improve function and prevent readmissions for this patient group. The Transition of Care Taxonomy was also developed in this study, which describes the 8 domains of a transitional care intervention.
Interventions for caregivers of patients with TBI 	[name] (Co-I of R03)	Systematic literature review	Studies showed mixed patterns of intervention effects on caregiver and patient outcomes; strength of evidence ranged from moderate to very low and intervention impact is inconclusive.
Neural correlates of personal goal activation 	[name] (Co-I of R03)	Event-related fMRI design	N = 75. Participants rapidly exposed to their self-identified goals had significant neural activation compared to exposure to yoked-control words. Findings extend understanding of how goals influence behavior.
Cognitive performance of adults with TBI 	[name] (Co-I of R03)	Experimental design	N = 44. Adults with TBI compared to matched healthy peers demonstrated social communication and discourse impairments that were influenced by the cognitive demands of the communication task.
Social communication of adults with TBI 	[name] (Co-I of R03)	Systematic literature review	Communication needs of adults with TBI should be prioritized and assessment approaches should be contextual and feasible.

Abbreviations: TBI = traumatic brain injury; ABI = acquired brain injury; med = medication; MI = myocardial infarction

**Ongoing Research Related to TBI Transitional Care.** [name] (PI of R03) is currently PI of an ongoing pilot award [co-investigator [name]] funded by Duke School of Nursing. The aim of the study is to obtain perspectives of patients with TBI, families, and providers on needs and goals during the transition from acute hospital care to home. Findings will inform development of the TBI transitional care intervention. [name] is currently co-investigator of the Comprehensive Post-Acute Stroke Services (COMPASS) study, a 40-site pragmatic trial funded by PCORI to assess the effectiveness of a comprehensive, evidence-based, post-acute care model on patient-centered outcomes for patients with stroke. Patients with stroke discharged from intervention hospitals receive a 2-day telephone follow-up; a comprehensive clinic visit within 2 weeks that includes a neurological evaluation; assessments of social and functional determinants of health; and an individualized care plan integrated with community-specific resources. Findings from [name] study will be used to inform the patient-centered portion of the TBI transitional care intervention. [name] is currently PI of

a retrospective study of factors contributing to cognitive-communication needs of adults with TBI. Findings will inform the patient-centered cognitive, communication, and social aspects of the TBI transitional care intervention. [name] is currently PI of HI-FIVES, an evidence-based skills training program for family caregivers of veterans referred to home care services, funded by a VA HSR&D grant, which is currently undergoing an 8-site RCT. HI-FIVES includes group classes for family caregivers to learn clinical, psychological, and support-seeking skills to improve caregiver functioning. Findings from [name] study will inform the family-centered key processes of the TBI transitional care intervention.

**Impact of Proposed Research.** Despite advances in transitional care, we are without data to inform development and testing of a TBI transitional care intervention that addresses specific needs and preferences of patients with TBI discharged home from acute hospital care and their family caregivers. Input from patients, families, and providers on the acceptability of an intervention of this nature is critical, as is data on the intervention's feasibility and preliminary efficacy. With this proposed work, by 2021, we will have assessed the feasibility, acceptability, and preliminary efficacy of a TBI transitional care intervention that aims to improve patient functional status, decrease caregiver strain, and direct patients and families to appropriate resources and care that is concordant with their health-related goals.

## C. INNOVATION

Our proposed work aims to develop a transitional care intervention to improve patient functional status and decrease caregiver strain. This research is novel as very little transitional care research addresses functional status or incorporates the needs of family caregivers. In addition, there is low strength of evidence for transitional care interventions to support patients with TBI discharged home from acute hospital care and families; our research aims to address the unique needs and preferences of this patient population. Finally, this study seeks to shift the paradigm of how care is provided to patients with TBI and families as they transition home, from interventions that separately focus on discharge preparation or on community needs to interventions that optimize and coordinate pre- and post-discharge care and needs to enhance care continuity.

## E. APPROACH

**Setting and Population.** All patients with TBI meeting inclusion criteria admitted to Duke University Hospital (DUH) neuro units 8W and 4100 and the 6 DUH medical-surgical/trauma units will be invited to participate in studies for aim 1 and 2. Collaborators on this award, [name], MD, neurologist and Vice Chair of Neurology Clinical Operations and [name], MD, trauma surgeon and Chief of Trauma and Critical Care Surgery, have agreed to facilitate recruitment from their respective areas (see letters of support).

**Inclusion Criteria.** Patients with TBI will be eligible if they meet the following requirements: a) age 18-64 years; b) diagnosed with moderate or severe TBI [admission Glasgow Coma Scale score of 3-12]; c) admitted to a DUH inpatient unit; d) plans to be discharged home from DUH; e) sufficient cognitive functioning to participate (i.e., able to follow 2-step commands), as determined by the Galveston Orientation and Amnesia Test (score  $\geq 76$  eligible); f) sufficient oral communication skills to participate, as determined by the Bedside Western Aphasia Battery-Revised (score  $\geq 93.8$  eligible); and g) English speaking (see Appendix A). [name] has successfully interviewed patients with TBI pre- and post-discharge with these criteria. Family members of patients with TBI will include biological relatives and friends and are eligible if they: a) are an anticipated primary caregiver after discharge (i.e., plans to live in same home as person or have direct contact with person  $\geq 10$  hours/week); b) age  $\geq 18$ ; and c) English speaking. Healthcare providers will be eligible if they: a) self-identify as a licensed provider and b) provide care to patients with TBI during the transition home (in hospital or within 8 weeks of discharge). All participants must be able to consent to participate.

**Sample Size Justification (Aim 1 and 2).** In Aim 1, we selected 45 to 60 total participants across 6 focus groups, guided by stage 1 of the NIH Stage Model for Intervention Development guidelines of including 15-30 participants per interviewee group (i.e., patients with TBI, family caregivers, providers). In accordance with historical qualitative research, we will hold  $\geq 3$  focus groups, each with 6-10 participants, to yield rich data. For Aim 2, we propose a reasonable sample size so we can sufficiently assess feasibility, acceptability, and preliminary efficacy of the intervention by using the rule of thumb of at least 12 participants per group for pilot studies. Our desired sample size for Aim 2 is 30 total participants (15 patient/family dyads) who complete the full intervention. Based on prospective TBI studies with follow up to one year, attrition can be up to 33% attrition. To be conservative, we plan to enroll 40 total participants (20 patient/family dyads), expecting 33% attrition, to reach our desired sample size of 30 total participants (15 patient/family dyads). We will recruit males and females and racial/ethnic minorities to explore sex- and racial/ethnicity-based differences. In 2018, DUH admitted 663 patients with TBI and discharged 380 patients with moderate-to-severe TBI (age  $< 65$

years) home from acute hospital care. Based on DUH estimates, a similar number should receive care annually. Typical recruitment of persons with TBI is  $\geq 50\%$ , leaving  $\geq 190$  patients/year and  $\geq 15$  patients/month to recruit. DUH does not collect family data, but research suggests family recruitment is  $\geq 50\%$ . [name] research shows pre-discharge recruitment of patients with TBI and family caregivers in another hospital system was  $\geq 60\%$ . DUH also employs  $\geq 100$  healthcare providers that care for patients with TBI during the transition (in the hospital or within 8 weeks of hospital discharge) for recruitment.

**Recruitment and Informed Consent (Aim 1 and 2).** DUH staff identified by clinical leaders specified above will identify eligible patients with TBI, family members, and healthcare providers and ask if the PI or research assistant may discuss the study with them. The PI or research assistant will then meet with the potential participant to inform them about the study. If the potential participant is interested in participating in the study, the PI or research assistant will walk the participant through the informed consent, clearly explaining the study purpose and planned activities and will answer all questions. Finally, the PI or research assistant will obtain a signed informed consent and will provide the participant with a copy for their own records. The primary threat to attrition in this study is loss to follow-up. To reduce and prevent attrition, participants will receive \$15 each after completion of each interview and each data collection time point.

**Aim 1 Study Overview.** We will use a combination of existing clinical guidelines, our prior and ongoing research, and a scoping review of care transitions literature to guide intervention development. Potential intervention components are described below in the section titled "Developing the Intervention (Aim 1)." We will create a manualized intervention protocol, which we will then refine with focus groups with patients with TBI, families, and healthcare providers. A trained research assistant will assist with intervention development and refinement. Intervention development (3 months) and refinement (6 months) will take 9 total months.

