selected components for our intervention (based on our prior/ongoing research). It is important to note that, to date, clinical guidelines and research (such as that of the NICE guidelines and Transition of Care Taxonomy) address system structural components and processes but does little to explore behavioral mechanisms that empower families and patients to follow-through with training and treatment plans. Drawing on [name] (co-investigator) expertise in behavioral modifications, the intervention we develop will incorporate behavioral change mechanisms to increase the likelihood that patients and families follow-through with training and treatment plans. The intervention's key processes will aim to improve patient functional status, caregiver strain, and to direct patients and families to appropriate resources and care that is concordant with their health-related goals. We will create a manualized, intervention protocol, which will take 3 months.

**Refining the Intervention (Aim 1).** The manualized intervention protocol will undergo iterative user-testing to determine acceptability.

The 6 focus groups (6-10 participants each) will use a stratified, purposive sample to obtain informational representation. Focus groups will be organized concordantly based on insurance status and group membership (patient, family, or healthcare provider). We will have one group with patients with TBI and family members with insurance and one group without; one group with

Table 3. Transition of Care Taxonomy (TCT) Domains and Intervention Components	
TCT Domain	Pre-selected Components
Transition Type	Acute hospital to home
Model Type	Hospital-initiated
Recipient(s)	Patient and family caregiver
Key Transitional Care Processes	Assessment of needs, patient/family education, goal setting, care coordination, referral to resources, and individualized care plan
Intervention Facilitators	Multi-disciplinary team (e.g., nurse, case manager/social worker, therapists, mental health counselor)
Contact Method	In-person home visit, clinic visit, and phone calls
Intensity and Complexity	In-person home visit 7 days post-discharge, weekly calls, and comprehensive clinic visit at 2 weeks post-discharge
Outcomes	Patient, proxy-, and family-reported outcomes (see Aim 1 and 2)

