only patients with TBI and one group with only family members; one group with healthcare providers who care for patients in hospital and one group with healthcare providers who care for patients with TBI after discharge. Individual interviews will be used if availability for a focus group becomes challenging. At each focus group, we will talk through the protocol and describe and show what the intervention could entail. We will ask participants to discuss if intervention components address their transition needs and goals (discharge process and first months at home) and components that are missing or need revision. We will also explore individual, cultural, and social factors that may influence transition needs such as individual experiences in the clinical encounter; cultural beliefs about healthcare, interaction with providers, and communication preferences; and social determinants such as economic stability after TBI, neighborhood environment, community resources, and access to post-TBI education, training, and providers. We will also establish, from the perspectives of the patients and families, additional secondary outcomes that matter the most to them. At the completion of the focus group, participants will complete a demographic questionnaire (Appendix B), including questions about age, sex, race/ethnicity, and education and employment; patients and families will also answer questions about the patient's injury cause and date, health insurance status, self-identified social economic status, pre- and post-injury living arrangements, and post-discharge support. Each focus group will be 90 minutes long.

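### Do six focus groups of 6 to 10 people fail to deliver the 45 to 60 participants, and the 15 per stakeholder type, that Aim 1 relies on?

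*Combined protocol and SAP*

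**What the plan says.** The Aim 1 numbers appear in three places.

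- **Specific Aim 1** plans "6 focus groups (total 45-60 people) of patients with TBI, families, and healthcare providers".
- **Section E, Sample Size Justification (Aim 1 and 2)** repeats the total ("we selected 45 to 60 total participants across 6 focus groups"). It gives as its guide an NIH stage-model recommendation of "including 15-30 participants per interviewee group (i.e., patients with TBI, family caregivers, providers"), and it describes "focus groups, each with 6-10 participants, to yield rich data".
- **Section E, Refining the Intervention (Aim 1)** restates the group size ("The 6 focus groups (6-10 participants each) will use a stratified, purposive sample") and sets the composition. Two groups mix patients and family: "We will have one group with patients with TBI and family members with insurance and one group without". Two are single-type: "only patients with TBI and one group with only family members". Two are for providers: "one group with healthcare providers who care for patients in hospital and one group with healthcare providers" seeing patients after discharge. Individual interviews are allowed where a focus group is hard to arrange.

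No section gives a minimum number per type or says how the mixed groups divide between patients and family members.

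**The concern.** The three ranges do not follow from one another. Six groups at the permitted minimum of 6 make 36 people, below the stated 45. Each type has the equivalent of two groups, so at that minimum there would be 12 providers, and 12 patients and 12 family members if the mixed groups divided evenly. All three counts are below the 15 used to justify the sample. If family members outnumbered patients in the mixed groups, patients, for whom the intervention is mainly built, could be the smallest voice in its refinement. The worry is that Aim 1 could finish smaller than its own justification, or lopsided, while each session kept to the group-size rule.

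**Working it through.** This is a counting check. Aim 1 is analysed by directed content analysis, so no power calculation applies.

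**Inputs.** 6 groups; 6 to 10 per group; 15 to 30 per type; 3 types; stated total 45 to 60 (Sample Size Justification). Two mixed, one patient-only, one family-only and two provider groups (Refining the Intervention).

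**Reproducing the stated 45 to 60.**
- Lower end: 3 types × 15 = 45.
- Upper end: 6 groups × 10 = 60.

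Both ends reproduce, but from different rules. Group size alone gives 6 × 6 = 36 to 6 × 10 = 60. The per-type guide alone gives 3 × 15 = 45 to 3 × 30 = 90. The stated total is where these two ranges overlap.

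**Mean group size needed.** 45 / 6 = 7.5 and 60 / 6 = 10, so the target needs groups averaging 7.5 to 10, which is within 6 to 10.

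**Counts by type from group size alone.**
- Providers: 2 × 6 = 12 to 2 × 10 = 20. This needs no further assumption.
- Patients, or family, with an even split of the mixed groups: 6 + 3 + 3 = 12 to 10 + 5 + 5 = 20.
- Patients, or family, with any split that leaves at least one of each type in a mixed group: 6 + 1 + 1 = 8 to 10 + 9 + 9 = 28.

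The range 12 to 20 is therefore exact for providers and conditional for the other two types.

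**Can all the limits hold together?** Yes. One layout:

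| Group | Size | Patients | Family | Providers |
|---|---|---|---|---|
| Patient-only | 8 | 8 | 0 | 0 |
| Family-only | 7 | 0 | 7 | 0 |
| Mixed 1 | 8 | 4 | 4 | 0 |
| Mixed 2 | 7 | 3 | 4 | 0 |
| Provider 1 | 7 | 0 | 0 | 7 |
| Provider 2 | 8 | 0 | 0 | 8 |
| Total | 45 | 15 | 15 | 15 |

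**Do group size and total together secure 15 per type?** No.
- Provider groups of 6 + 6 = 12, with 33 people in the other four groups (for example 8 + 8 + 8 + 9), total 45 with only 12 providers.
- All groups at 10 total 60, but one patient in each mixed group gives 10 + 1 + 1 = 12 patients.

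**Largest shortfalls at the group-size minimum.** Total: 45 − 36 = 9, or 9 / 45 = 20%. Providers: 15 − 12 = 3, or 3 / 15 = 20%.

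**The case for a change.** The strongest case for a change does not rest on the total. As the last two examples show, a team can respect both the group size and the 45 to 60 and still finish with 12 of one type. Imbalance is also plausible. Patients must pass cognitive and communication thresholds and be able to consent. The Potential Problems and Solutions paragraph expects that some will lack the cognitive capacity and relies on family input in that event. The interview fallback carries no number and no rule for counting interviewees toward a type. One sentence would settle all of this, and the plan's own projections (at least 15 patients a month to recruit, at least 100 providers) suggest it would be easy to meet.

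The wording gap is real, and that part stands. It does not amount to an error, for three reasons. The 15 to 30 is offered as guidance for choosing the sample, not as a binding floor. Composition is chosen deliberately under stratified, purposive sampling, so the team can see and correct a shortfall in one type while recruiting, by interview if necessary. And nothing in the documents suggests that 12 providers or patients instead of 15 would alter how the content analysis refines the intervention.

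The obvious remedy, groups of 8 to 10 with equal halves in the mixed groups, would be stricter than the plan needs. It raises the minimum total to 6 × 8 = 48, so samples of 45 to 47 that now comply would not, and a group of 9 cannot be halved.

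**Conclusion.** No change is called for. The counts of 36 to 60 in total and 12 to 20 providers are right, but they are what group size allows taken alone. The plan also states a total of 45 to 60, which lies inside that range and can be met with 15 of each type. No stated figure is miscalculated and no two statements conflict.

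The remaining gap is an unwritten minimum per type and an unwritten split of the mixed groups. At the smallest permitted group size it is worth 3 providers (12 against 15). For patients or family it is also 3 with an even split, and at most 7 (8 against 15) under the most lopsided split. That last case assumes a single-type group of 6, two mixed groups and at least one person of each type in each mixed group; interviews could only add to it.

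The conclusion rests on reading the 45 to 60 as the recruitment target, the 6 to 10 as the tolerance for one session, and the 15 to 30 as guidance. Aim 1 is qualitative, so no error rate, precision or reported estimate depends on these counts. Keeping a running tally by type is ordinary practice in purposive recruitment and needs no change to the plan.
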